## **Qualitative Protocol Development Tool**

The research protocol forms an essential part of a research project. It is a full description of the research study and will act as a 'manual' for members of the research team to ensure adherence to the methods outlined. As the study gets underway, it can then be used to monitor the study's progress and evaluate its outcomes.

The protocol should go into as much detail about the research project as possible, to enable the review bodies to fully understand your study.

The use of this collated consensus guidance and template is not mandatory. The guidance and template are published as standards to encourage and enable responsible research.

The document will:

- Support researchers developing protocols where the sponsor does not already use a template
- Support sponsors wishing to develop template protocols in line with national guidance
- Support sponsors to review their existing protocol template to ensure that it is in line with national guidance.

A protocol which contains all the elements that review bodies consider is less likely to be delayed during the review process because there will be less likelihood that the review body will require clarification from the applicant.

We would appreciate self-declaration of how you've used this template so we are able to measure its uptake.

Please indicate the compatibility of this template with any existing templates you already use by stating one of the following on the front of each submitted protocol:

- **This protocol has regard for the HRA guidance and order of content; OR**
- **This protocol has regard for the HRA guidance; OR**
- **This protocol does not have regard to the HRA guidance and order of content**

## STUDY SUMMARY

It may be useful to include a brief synopsis of the study for quick reference. Complete information and, if required, add additional rows.

Study Title	ReHabGame: A Markerless, Game-Based Rehabilitation program
Internal ref. no. (or short title)	ReHabGame

Study Design	
Parallel, two-cohort (Neurological, MSK), two-arm RCT
 
Arms (within each cohort):
 
 
1. Usual Care only
 
2. Combined ReHabGame + Usual Care
 

Study Participants	
 
• Age 18+ years
 
• Ability to follow simple instructions and give consent
 
• No severe cognitive impairment (MoCA <math>\geq 22</math>)
 
• Stable medical condition (no recent cardiovascular event)
 

Planned Size of Sample (if applicable)	
Planned Sample Size per cohort (Neurological or MSK):
 
23 participants per arm: 2 arms = 46 participants
 
Total across both cohorts:
 
46 (Neurological) + 46 (MSK) = 92 participants
 
Allowing for ~20% attrition,

Follow up duration (if applicable)	4-week post-intervention follow-up (Week 12)
Planned Study Period	
Participants to be randomised to:
 
 
1. ReHabGame: 30–45 min sessions, 2x/week for 6–8 weeks
 
2. Usual care: standard physio sessions, 2x/week for 6–8 weeks
 

Research Question/Aim(s)	
Primary Objectives: feasibility endpoints
 
(Combined = ReHabGame + usual care; Control = usual care only)
 
 
• Neurological cohort:
 

	
 
○ Compare change in FMA-UE score from baseline to week 8 between arms
 
• MSK cohort: 
 
○ Compare change in SPADI score from baseline to week 8 between arms
 
 
 
 
Secondary Objectives: clinical outcomes
 
 
• Within each cohort, compare between-arm differences in: 
 
○ Adherence & Engagement: session attendance, System Usability Scale (SUS)
 
○ Functional Independence: Barthel Index (neurological), DASH (MSK)
 
○ Pain & ROM (MSK only): VAS pain, goniometric ROM
 
○ Motion-tracking metrics: accuracy, smoothness, range captured by Kinect
 
 
 
 
Exploratory Objectives
 
 
• Cost and resource use (therapist time, equipment) across arms
 
• Participant satisfaction and motivation (mixed-methods interviews)
 
• Barriers/facilitators to implementing gamified rehab
 

--	--

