#### Analysis:

- Analysis of covariance (ANCOVA) with Week 8 score as dependent variable, adjusting for:
  1. Baseline score
  2. Age
  3. Sex
  4. Randomisation stratum (high vs low severity)
- Report adjusted mean difference at Week 8 with 95% CI and p-value

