## 4.2 Outcome

**Broad Outcome:** A clearer understanding of how a markerless, game-based rehabilitation system affects upper-limb motor recovery, motivation, and overall functional independence.

**Practical Impact:** Evidence to support (or refute) the use of ReHabGame as a routine therapeutic tool, potentially informing clinical guidelines and future technology-driven rehabilitation strategies.

After each gamified rehabilitation session, participants will receive personalised, visual performance feedback generated by the ReHabGame platform. This includes:

- A PDF-based summary showing:
  - Percentage of movement types (e.g. abduction, adduction of the upper arm)
  - Distribution of virtual objects around the participant in the game environment
  - Visual markers of target reach, joint usage, and task completion
- Feedback is presented immediately post-session in a simple, colour-coded format that participants can understand without technical expertise.

A member of the research team will review this feedback in person with the participant to:

- Celebrate progress and encourage engagement
- Clarify what the data means in lay terms
- Address any confusion or concern
- Adjust future gameplay settings if needed to support optimal challenge and safety

The ReHabGame system uses an **automated, performance-based algorithm** to dynamically adjust the difficulty level of gameplay in real time. This ensures that exercises remain **appropriately challenging, engaging, and within the user's capabilities**, thereby reducing frustration and promoting sustained participation.

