### **7.2.1 Size of sample**

Allocated as follows:

- o Per cohort: 46 participants
- o Per arm (1:1): 23 participants
- o Expected completers per arm:  $\geq 18$  participants
- o Total completers:  $\geq 72$  participants

This sample size is not powered for definitive hypothesis testing but is sufficient to:

1. Estimate recruitment, retention, and adherence rates with acceptable precision.
2. Generate variance estimates for the primary outcomes (FMA-UE in the Neurological cohort; SPADI in the MSK cohort) to inform sample-size calculations for a future definitive trial.

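### The primary objective is labelled feasibility but consists of two efficacy comparisons, and the protocol promises conclusions on routine use that its own stated purpose and size do not support

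*Protocol*

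**What the plan says.** **What is labelled primary.** The Study Summary gives the primary objectives the label "feasibility endpoints". Two items follow: "Compare change in FMA-UE score from baseline to week 8 between arms" for the neurological cohort and "Compare change in SPADI score from baseline to week 8 between arms" for the MSK cohort. The next block carries the label "Secondary Objectives: clinical outcomes", although it includes session attendance and the usability scale. Under Outcome Measures, a further version of the primary objective speaks of the feasibility of the system in improving recovery, which merges the two ideas.

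**What is analysed as primary.** Section 4.1 poses both primary questions as whether the combined arm improves more than usual care. Planned Statistical Analyses item 2 and the Section 5 table name FMA-UE and SPADI as primary outcomes. The opening of Planned Statistical Analyses sets two-sided alpha at 0.05, and item 2 ends with the instruction "Report adjusted mean difference at Week 8 with 95% CI and p-value". Recruitment, retention and completeness stand under a separate Feasibility Objectives heading in Section 4.1, and as descriptive metrics in both analysis sections.

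**What the trial is said to be for.** Planned Statistical Analyses item 7 calls it a feasibility pilot. Section 7.2.1 says: "This sample size is not powered for definitive hypothesis testing but is sufficient to" estimate recruitment, retention and adherence rates and the variances needed for a later trial. Section 4.2, however, names as its practical impact "Evidence to support (or refute) the use of ReHabGame as a routine therapeutic tool". The last paragraph of Section 2 promises strong evidence on how to deploy gamified rehabilitation.

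**The concern.** A reader cannot tell which result decides this study. One heading says feasibility, while the content and the analysis sections say efficacy. With both versions in the approved text, either the feasibility rates or a favourable efficacy p-value could later be presented as the primary result, and each choice could cite the protocol. That leaves room for selective reporting.

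The claims also go beyond the stated purpose. A trial sized to estimate rates and variances cannot also undertake to settle whether the system should be used routinely, least of all in the negative direction.

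**Working it through.** **Step 1: the texts side by side.**

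| Place in protocol | Primary matter |
|---|---|
| Study Summary, label | Feasibility |
| Study Summary, items listed | Between-arm FMA-UE and SPADI change |
| Outcome Measures, Primary Objective | Feasibility and improvement merged |
| Section 4.1, primary questions | Superiority on FMA-UE and SPADI |
| Planned Statistical Analyses item 2; Section 5 table and item 2 | FMA-UE and SPADI by ANCOVA |
| Planned Statistical Analyses item 7; Section 7.2.1 | Feasibility pilot; rates and variances |

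These cannot all be right. This step needs no assumption.

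**Step 2: completers.** Section 7.2.1 expects at least 18 per arm and 72 in total. From 23 per arm with 20% attrition, 23 × 0.80 = 18.4, so 18 per arm and 4 × 18 = 72. The figure reproduces. Two other statements conflict with it. Section 7 expects at least 90 completers from 92, but 92 × 0.80 = 73.6. Section 7.2 recruits 108, which is 27 per arm and 27 × 0.80 = 21.6 completers. I therefore show 18 and 23 per arm, a range that covers all three.

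**Step 3: power.** The protocol gives no effect size, SD or baseline correlation. I assume d = 0.3 to 0.8 SD and r = 0 (unadjusted), 0.5 or 0.7. Power comes from the noncentral t with noncentrality [d / √(1 − r²)] × √(n/2). Degrees of freedom are 2n − 2 unadjusted and 2n − 6 with the four planned covariates, at two-sided alpha 0.05.

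| n per arm | d | Unadjusted | r = 0.5 | r = 0.7 |
|---|---|---|---|---|
| 18 | 0.3 | 14% | 17% | 23% |
| 18 | 0.5 | 31% | 39% | 53% |
| 18 | 0.8 | 65% | 76% | 90% |
| 23 | 0.3 | 17% | 21% | 28% |
| 23 | 0.5 | 38% | 48% | 64% |
| 23 | 0.8 | 76% | 86% | 96% |

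**Step 4: precision.** The 95% CI half-width in SD units is t × √(2/n) × √(1 − r²). For n = 18, √(2/18) = 0.333:
- unadjusted: 2.032 × 0.333 = 0.68
- r = 0.5: 2.042 × 0.333 × 0.866 = 0.59
- r = 0.7: 2.042 × 0.333 × 0.714 = 0.49

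The interval contains a 0.5 SD benefit unless the estimate falls below 0.5 minus the half-width: −0.18, −0.09 and +0.01 SD respectively. A non-significant but favourable estimate would therefore almost always leave a moderate benefit open.

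**Step 5: what the sample can estimate.** If 37 of 46 participants in a cohort (80%) complete Week 8, the Wilson 95% interval for retention is 67% to 89%. That is wide, but it is the kind of quantity Section 7.2.1 says the sample is for.

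**The case against.** The best defence is that pilots may report efficacy estimates, and that this protocol already limits how they should be read. It disclaims power, calls itself a pilot, and puts feasibility metrics first in both analysis sections. Section 5, item 2, asks only for the adjusted difference and its interval. The power figures mostly quantify what Section 7.2.1 concedes. For a large effect (0.8 SD) with strong baseline correlation, power would be respectable. All of this stands. It does not resolve the conflicting labels, and the disclaimer is itself one side of the conflict with Sections 2 and 4.2.

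A reader might go further in four ways that the documents do not support:

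- **The trial will be judged on two p-values, and a null result will count against the system.** That is a prediction. No decision rule links significance to the statement in Section 4.2.
- **Two tests at 0.05 inflate the false-positive rate to 1 − 0.95² = 9.75%.** The cohorts are different populations at different sites, with different instruments and separate analyses and questions. Nothing claims success if either one is positive.
- **The lack of progression thresholds, or the order of the lists, is an error.** The first is an omission and the second a matter of layout. Neither contradicts anything.
- **Thresholds can be read off the plan.** The 20% attrition figure is a planning allowance, and 75% attendance defines the per-protocol set. A monthly recruitment target would depend on whether 92 or 108 is meant.

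**Conclusion.** The point holds as a contradiction within the protocol, together with claims that exceed its stated purpose. The contradiction rests on the text alone. Its practical size rests on assumed effect sizes and correlations. At 0.5 SD with 18 completers per arm, power runs from 31% unadjusted to 53% at r = 0.7, so even in the most favourable of these cases a true moderate benefit would be missed nearly half the time. Having all 23 per arm complete raises the range only to 38% to 64%. The promise to refute cannot be kept on non-significance alone.

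This does not show that the sample is too small for a pilot, or that FMA-UE and SPADI should not be compared between arms. Nor is it a matter for a separate analysis plan, because the conflict lies in the protocol's own objectives.

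**What to change.** State one primary objective and use it everywhere. The choice that fits Section 7.2.1 and the description as a feasibility pilot is:

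- **Primary, in each cohort:** recruitment, Week 8 retention, adherence and data completeness, all already planned for collection.
- **Main clinical outcomes:** FMA-UE and SPADI, reported as adjusted differences with 95% intervals and read as estimates, not confirmatory tests.

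Carry this through the Study Summary; Outcome Measures; the opening and item 2 of Planned Statistical Analyses (alpha and p-value wording included); Sections 4 and 4.1, with the Feasibility Objectives; the Section 5 table and its item 2; Section 7.2.1; and the effectiveness wording at the start of Section 8. Remove the support-or-refute promise from Section 4.2 and the deployment claim from the end of Section 2.

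If the sponsor wants progression thresholds, it should choose and justify them after reconciling the totals of 92 (Section 7) and 108 (Section 7.2).

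The other consistent repair is an efficacy trial with a justified sample size. By the normal approximation, unadjusted 80% power at an assumed 0.5 SD needs 63 completers per arm in each cohort, against 18 expected, so that would be a different study.

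The recommended change costs wording only: same data, visits and participants. The sponsor gives up a headline efficacy claim that the sample cannot carry.

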## FUNDING AND SUPPORT IN KIND

FUNDER(S)	FINANCIAL AND NON FINANCIAL SUPPORT GIVEN
(Names and contact details of ALL organisations providing funding and/or support in kind for this study)	
Anglia Ruskin University	Financial and non-financial support

## **ROLE OF STUDY SPONSOR AND FUNDER**

Anglia Ruskin University serves as the study sponsor, providing overall responsibility for initiating, managing, and overseeing the trial. The sponsor's role includes ensuring adherence to the protocol, monitoring progress, and maintaining compliance with ethical and regulatory requirements. The internal institutional grant provides financial support but does not influence the study design, conduct, data analysis, interpretation, or dissemination of results. Final decisions regarding publication and reporting rest with the principal investigators, ensuring the integrity and independence of the research.

## **ROLES AND RESPONSIBILITIES OF STUDY MANAGEMENT COMMITTEES/GROUPS & INDIVIDUALS**

### **Study Steering Groups**

#### **Study Management Committees/Groups**

These committees and groups oversee the planning, implementation, and execution of the research project. Their responsibilities include:

- Ensuring adherence to ethical and regulatory standards.
- Providing guidance and oversight to research teams.
- Reviewing study protocols and procedures.
- Monitoring progress and addressing any issues or challenges that arise.
- Facilitating communication and collaboration among research team members.
- Reviewing and approving study-related documents, such as informed consent forms and data management plans.

#### **Individuals**

- Principal Investigator (PI):
  - Leads the research project and is responsible for its overall direction and management.
  - Develops the research protocol and obtains necessary approvals.
  - Supervises research team members and coordinates their activities.
  - Ensures compliance with regulatory requirements and ethical guidelines.
  - Analyses and interprets study data.
  - Reports study findings to relevant stakeholders.
- Research Team Members:
  - Co-investigators: Collaborate with the PI on specific aspects of the research project.
  - Research Assistants: Assist in data collection, analysis, publication, reporting, and other research activities.
  - Data Managers: Organize and manage study data.
  - Study Coordinators: Coordinate various aspects of the research project, such as liaising with the gatekeepers for participant recruitment and scheduling.
- Study Participants:
  - Contribute valuable data and insights by completing questionnaires, or providing other forms of information.

- Their involvement is essential for achieving the study objectives and generating meaningful findings.

**Independence:** The PPI Group operates as an advisory body, offering perspectives distinct from those of the research team. They do not control final decisions but strongly influence study conduct to ensure alignment with patient needs and priorities.

## PROTOCOL CONTRIBUTORS

### Principal Investigator

- Led the development of the research protocol, ensuring alignment with the study objectives and ethical guidelines.
- Developed the data analysis plan, including sample size calculations and statistical methods.
- Reviewed the protocol for methodological rigor and feasibility.
- Coordinated input from co-investigators and other team members.

### Co-Investigators

- Provided subject matter expertise, contributed to study design, and advised on methodological considerations.
- Assisted in drafting specific sections of the protocol (e.g., data collection procedures, outcome measures).

### Sponsor Representative

[figure not shown]
- Ensured compliance with institutional policies, funding requirements, and regulatory standards.
- Offered final approval for protocol submission.
- Patient/Public Involvement (PPI) Representatives
- Reviewed participant-facing documents to enhance clarity and relevance.
- Offered insights on study procedures to improve participant experience and engagement.

### KEY WORDS:

- Game-Based Rehabilitation
- Markerless Motion Capture
- Virtual Rehabilitation

## STUDY FLOW CHART

- Screen → Consent → Baseline (cohort-specific tests)
- 1:1 Randomisation into Game+ Usual-care, & Usual-care
- 6–8 week intervention (2 sessions/week)
- Assessments at Week 4 (interim), Week 8 (end), Week 12 (follow-up)
- Data analysis & dissemination

## Study Timeline and Procedures

The therapist collects feedback and shares their recommendations in a written format with the research team. This may include a brief interview or written feedback on usability, motivation, and any perceived barriers.

### 1. Screening & Consent (Week 0)

- Therapist confirms diagnosis and eligibility.
- Patient to review and sign the consent form (**via the above Link**).
- Assign study ID or name via the ReHabGame platform and keep the same name/ID though out the trial.
- Baseline functional test administered by an assessor.
- Randomisation occurs immediately afterward.

### 3. Intervention Sessions (Weeks 1–8): Questionnaire at week 2, 4, 8 (**via the above Link**)

- Combined arm only; 2x/week, Weeks 1–8

Usual care only:

- o 30–45 min therapist-led physiotherapy per session
- o 2 sessions/week for 6–8 weeks (standardised protocol)
- **Combined care- Usual-care + ReHabGame:**
  - o 30–45 min Kinect-guided exercises per session.
  - o Real-time difficulty adaptation; metrics auto-logged.
  - o Both modalities, each 2x/week (on separate days or back-to-back).
  - o Each session is logged in the PDF format.

#### 4. Mid-Point Assessment (week 4)

Quick re-test of the cohort's primary functional score (FMA-UE subset or SPADI). Assessments occur at Week 1 (if applicable), Week 4 (interim), Week 8 (end), and Week 12 (follow-up).

Kinect captures a snapshot of your movement metrics.

#### 5. End-Of-Intervention Assessment (Week 8)

- Full repeat of baseline tests supervised by a clinician the above link can be used “*ReHabGame: Assessments at Week 4 (interim), Week 8 (end), Week 12 (follow-up)*”.
- Patients receive session report PDF summarising all movement metrics over the course of the study.

#### 6. Follow-Up (Week 12)

- Final SUS and engagement surveys to gauge lasting impressions.
- Update on any late-emerging adverse events.
- Optional brief functional check to see if gains were maintained.
- We remind you how to request the lay summary of overall study findings.

### Outcome Measures

#### Primary Objective

Evaluate feasibility of ReHabGame in improving motor recovery and functional independence in:

1. Neurological cohort
2. MSK cohort

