### 1. Descriptive / Feasibility Metrics

- **Recruitment rate:**
  - Number screened, number eligible, number randomised (%)
- **Retention & adherence:**
  - Proportion completing Week 8 assessment in each arm (%)
  - Mean ( $\pm SD$ ) number of sessions attended per arm
- **Data completeness:**
  - Proportion of missing outcome data at each timepoint

These will be reported as counts, percentages, and 95% confidence intervals.

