## 7 SAMPLE AND RECRUITMENT

This pilot RCT will recruit 92 participants (46 per cohort), allowing for ~20% attrition to achieve at least 90 completers in total. Recruitment will take place over 12 months across two sites (neurorehabilitation and orthopaedic physio clinics).

- **Recruitment sources:**
  - Referrals from participating physiotherapists and neurologists
  - Clinic screening of outpatient caseloads
  - Posters and leaflets in waiting areas
  - Direct approach **via the treating clinician** during routine appointments; research staff contact patients only **after clinician referral and consent to be contacted**.

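### Feasibility is stated as the primary objective, but no rate is fixed in advance as not feasible, and other sections name FMA-UE and SPADI comparisons as primary

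*Protocol*

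**What the plan says.** **Feasibility as primary.** Under Outcome Measures, the Primary Objective is to "Evaluate feasibility of ReHabGame in improving motor recovery and functional independence", for the neurological and the MSK cohort. The Study Summary labels the primary objectives "feasibility endpoints", and the Interim Analyses paragraph calls the trial a feasibility pilot.

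**How feasibility is analysed.** Planned Statistical Analyses, item 1, lists recruitment, retention, sessions attended and data completeness, and adds: "These will be reported as counts, percentages, and 95% confidence intervals". The Feasibility & Descriptive Statistics item in section 5 does the same. The Feasibility Objectives in section 4.1 ask for estimates of recruitment, retention and completeness, an evaluation of whether randomisation is acceptable, and variance estimates.

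**Clinical outcomes as primary.** Directly under the feasibility label, the Study Summary lists between-arm comparisons of FMA-UE and SPADI change. Planned Statistical Analyses, item 2, names these as the Primary Outcomes, and section 4.1 makes them the Primary Research Questions.

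**Sample size.** Section 7.2.1 gives "Per cohort: 46 participants" and "Per arm (1:1): 23 participants", with at least 18 expected completers per arm and 72 in total. It says the sample is not powered for definitive hypothesis testing. It gives as purposes the estimation of rates and of variances, the latter "to inform sample-size calculations for a future definitive trial". Section 7 states "Recruitment will take place over 12 months across two sites" and describes 92 participants "allowing for ~20% attrition to achieve at least 90 completers in total". Section 7.2 says 108 will be recruited.

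**The concern.** A feasibility objective is usually meant to support a decision: proceed, change something, or stop. Here no recruitment, retention or adherence figure is tied to any of these. The nearest numbers do other work. The 18 and 72 completers are expectations with no consequence attached. The bar of 75% of sessions decides whether one participant enters the per-protocol set. The review by the Data Monitoring Committee covers safety only.

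Once the rates are seen, almost any of them can be described as feasible, and a cut-off chosen then carries no weight. Analysts cannot repair this later. Meanwhile the plan does fix two-sided tests at 0.05, with p-values, for FMA-UE and SPADI. The only results with a pre-specified threshold therefore concern the question that the protocol says it is not powered to answer definitively, and the feasibility questions, which the sample can address better, have none.

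**Working it through.** **1. The protocol's own completer figures.** Inputs: 23 per arm, four arms across two cohorts, about 20% attrition (sections 7 and 7.2.1).

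- Per arm: 23 × 0.80 = 18.4, so 18. Total: 4 × 18 = 72. Section 7.2.1 reproduces.
- Section 7's 90 completers does not: 92 × 0.80 = 73.6. Ninety of 92 means attrition of 2/92 = 2.2%.
- Section 7.2's 108 equals 90 × 1.2. At 20% attrition it yields 108 × 0.80 = 86.4 completers. Ninety completers would need 90/0.80 = 112.5, so 113 enrolled.

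The documents therefore hold three completer or recruitment targets that do not agree. None can serve as a benchmark until they are reconciled.

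**2. What the present plan would report.** Clopper-Pearson 95% intervals for Week 8 retention in one cohort:

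- 37/46 = 80%: 66% to 91%
- 28/46 = 61%: 45% to 75%

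The two reports would show different numbers, but no stated rule would lead to different conclusions.

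**3. Could 46 per cohort support a retention rule?** For a rule that says go if at least r of n complete, P(go) = P(X ≥ r), with X binomial(n, p). The upper rate of 80% follows from the planned attrition of about 20%. All lower rates, and 85%, are assumptions.

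| Rule | P(go) at the lower rate | P(go) at the upper rate |
|---|---|---|
| ≥34/46 | 0.035 at 60% | 0.886 at 80% |
| ≥36/46 | 0.038 at 65% | 0.926 at 85% |
| ≥36/46 | 0.038 at 65% | 0.694 at 80% |
| ≥38/46 | 0.039 at 70% | 0.754 at 85% |
| ≥38/46 | 0.039 at 70% | 0.412 at 80% |

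With a false-go probability of at most 0.05, rates 20 points apart separate well, 15 points is marginal, and 10 points fails.

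A stop boundary needs the same check. Stopping below 28/46 has probability 0.48 at a true 60%, 0.23 at 65% and 0.0008 at 80%. It rarely stops a good cohort, but it misses about half of those at 60%.

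**4. Adherence to game sessions.** Only the combined arm has these, so n = 23 per cohort. Let p be the proportion of participants who reach the adherence bar.

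| Rule | p = 50% | p = 60% | p = 80% |
|---|---|---|---|
| ≥16/23 | 0.047 | 0.24 | 0.93 |
| ≥18/23 | 0.005 | 0.054 | 0.695 |

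Neither rule separates 60% from 80% well.

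The number of prescribed sessions is also unsettled. The Intervention Sessions text gives the game twice weekly in Weeks 1 to 8 (2 × 8 = 16) and elsewhere 6 to 8 weeks at twice weekly (12 to 16). The ReHabGame Intervention item under Staff Training allows 1 to 2 per week over 6 to 8 weeks (6 to 16). Seventy-five per cent of that is anywhere from 4.5 to 12 sessions.

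**5. Recruitment.** Forty-six is the target, not the denominator. A recruitment criterion compares the number randomised in 12 months with 46, or uses the number screened or eligible as denominator. The binomial figures above do not apply to it.

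**The case against.** The strongest reply is that the feasibility aims are aims of estimation. Section 4.1 asks for estimates, section 7.2.1 speaks of precision, and both analysis sections report intervals. These agree with each other, and an estimate answers an estimation aim without a pass mark. A go/stop rule is then a design preference. It can also be said that the Primary Objective concerns feasibility in improving motor recovery and function, which is not obviously a retention question, and that other sections make FMA-UE and SPADI primary.

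Much of this stands. It is why the point cannot be that the trial plainly fails its one primary objective: the protocol has not settled which objective that is. What remains is that where feasibility is called primary, it is to be evaluated, and no standard for the evaluation is given. An unseen statistical analysis plan does not change how the protocol itself fixes its primary objective.

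Three stronger readings are tempting and unsupported:

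- **That a definitive trial will follow whatever the pilot shows.** The protocol says only that variance estimates will inform a sample-size calculation, and section 4.2 allows for evidence against routine use.
- **That the Week 8 p-values will decide progression.** No section says so. The protocol leaves that possibility open.
- **That 46 per cohort is enough for a go/stop rule in general.** It is enough for retention at about 20 points' separation. It does not carry over to adherence or recruitment.

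**Conclusion.** The point holds in limited form. Feasibility is stated as the primary objective, no recruitment, retention or adherence rate is fixed in advance as not feasible, and any verdict would be post hoc. The conflict over which objective is primary is part of the same fault.

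For size: with 46 per cohort, a retention rule of 34 or more gives P(go) 0.89 at 80% and 0.035 at 60%, so a usable criterion is affordable at the planned sample size. This rests on independent binomial outcomes, on 80% taken from the planned attrition, and on 60% as an assumed unacceptable rate that appears nowhere in the protocol. If the sponsor regards 70% as unacceptable, the same sample gives a go probability of only 0.41 at 80%. The data would remain usable without the change. What is lost is a pre-specified conclusion on feasibility.

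**What to change.** 1. State once which objective is primary, and align the Study Summary, Outcome Measures, Planned Statistical Analyses and section 4.1 with it.
2. If it is feasibility, add to the Primary Objective and to the feasibility analysis, per cohort and before recruitment starts, go, amend and stop criteria for Week 8 retention, for game-session adherence in the combined arm, and for the number randomised in 12 months against the planned 46. Show the go and stop probabilities for each criterion. The retention rule of 34/46 above is an illustration, and the sponsor should set the final cut-offs.
3. Before using them as benchmarks, reconcile the completer and recruitment targets in sections 7, 7.2 and 7.2.1.
4. Reconcile the session frequency and duration between the Intervention Sessions text and the item under Staff Training, so that adherence has a fixed denominator, and say whether it counts game sessions only.
5. State that progression rests on these criteria and not on the Week 8 p-values.

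The cost is protocol wording, with no new data or participants. The downside is that the pilot can then formally fail a criterion.
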